3.1.1. Part A (Single Ascending Dose)

Part A will comprise a single-dose, sequential group, escalating-dose design conducted in healthy adult male and female subjects; also incorporating a single-group, 2-period crossover arm investigating the effect of dosing AQ280 with food compared to dosing in the fasting condition. The first dose level administered is planned to be 3 mg AQ280.

A total of approximately 40 subjects are planned to be studied in 5 groups (Groups A1 to A5; with one of the groups including the food effect evaluation). In each group, 6 subjects will receive AQ280 and 2 subjects will receive placebo. The dose will be administered in the fasted state in accordance with the randomization schedule on the morning of Day 1 for all groups, including Period 1 for the food effect evaluation group (see [Section 3.1.1.1](#) for additional food-evaluation group requirements). Each group should contain both male and female subjects, preferably at least 2 subjects of each gender. Additional groups may be added based on the need for more evaluations or groups removed based on data obtained.

The first group in Part A will be divided into 2 cohorts, with each cohort being dosed at least 24 hours apart. The first cohort will comprise 2 subjects, with 1 subject receiving AQ280 and 1 subject receiving placebo. The second cohort will comprise 6 subjects, with 5 subjects receiving AQ280 and 1 subject receiving placebo. The 2 sentinel subjects (first cohort) will be dosed at least 24 hours before the second cohort of 6 subjects. Dosing of subjects in the second cohort will not occur if any of the dose escalation stopping criteria ([Section 3.7](#)) are met by the 2 sentinel subjects. Circumstances under which sentinel dosing may be introduced in other groups are detailed in [Section 3.4.1](#).

There will be a minimum of 9 days between dose escalations for each group.

Potential subjects will be screened to assess their eligibility to enter the study from 2 days up to 5 weeks before the dose of AQ280 or placebo. Each subject will participate in 1 group only and will reside at the study site from Day -1 (the day before dosing) to Day 3 of the treatment period, with dose administration occurring on Day 1. A safety follow-up phone call will be conducted 1 week (± 2 days) after dosing.

Each eligible subject will participate in 1 treatment period only, except for the food effect group, where each subject will participate in 2 treatment periods.

[figure not shown]

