3.4.1. Dose Interval

Following thorough review of all available nonclinical data (pharmacological and toxicological), dosing for the starting dose level in Part A (Group A) will be such that 2 subjects (1 AQ280 and 1 placebo) will be dosed at least 24 hours before the remaining 6 subjects.

At least 3 JAK inhibitors are approved for clinical use and several others are in Phase 3 clinical development. Thus, the risk of on-target suspected unexpected serious adverse reactions will be negligible. To minimize the consequence of any potential unknown off-target toxicity, sentinel dosing will be implemented for the first SAD group in Part A. Based on knowledge of the pharmacodynamic (PD) effects of other JAK inhibitors, in particular the JAK1-selective inhibitor abrocitinib, no effects are expected from a single dose beyond 24 hours after dosing. Therefore, a 24-hour interval between dosing of the sentinel subjects and the remaining subjects in the first group is considered sufficient, after review of available safety data.

Because of the well described target pharmacology and safety of other JAK inhibitors, sentinel dosing is not considered necessary for Part B, in which the predicted exposure will not exceed an exposure already shown to be safe and well tolerated in Part A.

Sentinel dosing may be introduced in other groups than in the first SAD group under the following circumstances:

- In case of any emerging clinical signs or AEs that do not meet stopping criteria but in the opinion of the DEC warrant a more cautious dose escalation.
- In case of non-linear PK that warrants a more cautious dose escalation.
- If the exposure is expected to exceed the NOAEL exposure in dogs, in which case further dose escalation will require a substantial protocol amendment.

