5.3. Randomization

The randomization code will be produced by the statistics department at Labcorp Drug Development using a computer-generated pseudo-random permutation procedure.

In Parts A and B, 2 subjects in each group will be randomly assigned to receive placebo.

For the first group in Part A (Group A1), sentinel dosing will occur whereby 2 subjects (1 active and 1 placebo) will be dosed on 1 day and, providing no safety concerns arise, the remaining 6 subjects will be dosed at least 24 hours later.

Subjects in the food effect evaluation group in Part A will receive the same treatment in Treatment Periods 1 and 2.

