Appendix 3: Total Blood Volume

The following blood volumes will be withdrawn for each subject in Part A (single ascending dose).

	Volume per blood sample (mL)	Maximum number of blood samples	Total amount of blood (mL)
Full clinical laboratory evaluations	9.3	4	37.2
Serology	3.5	1	3.5
Quantiferon™ TB Gold test	4	1	4
AQ280/AQ282 PK ^a	4	17	68
CCI [REDACTED]	2	8	16
CCI [REDACTED] PD ^{a,b}	2.5	8	20
Total:			148.7

Abbreviations: PD = pharmacodynamics; PK = pharmacokinetics; TB = tuberculosis.

^a Includes 3 potential additional samples.

^b Additional assessments performed outside of full clinical laboratory evaluations.

The following blood volumes will be withdrawn for each subject in Part A (single ascending dose) for the food effect evaluation.

	Volume per blood sample (mL)	Maximum number of blood samples	Total amount of blood (mL)
Full clinical laboratory evaluations	9.3	7	65.1
Serology	3.5	1	3.5
Quantiferon™ TB Gold test	4	1	4
AQ280/AQ282 PK ^a	4	34	136
CCI [REDACTED]	2	8	16
CCI [REDACTED] PD ^{a,b}	2.5	8	20
Total:			244.6

Abbreviations: PD = pharmacodynamics; PK = pharmacokinetics; TB = tuberculosis.

^a Includes 3 potential additional samples per treatment period.

^b Additional assessments performed outside of full clinical laboratory evaluations.

If extra blood samples are required, the maximum blood volume to be withdrawn per subject will not exceed 550 mL.

The following blood volumes will be withdrawn for each subject in Part B (multiple ascending dose).

	Volume per blood sample (mL)	Maximum number of blood samples	Total amount of blood (mL)
Full clinical laboratory evaluations	9.3	7	65.1
Serology	3.5	1	3.5
Quantiferon™ TB Gold test	4	1	4
AQ280/AQ282 PK ^a	4	32	128
CCI [REDACTED] [REDACTED] [REDACTED] PD ^{a,b}	2	5	10
CCI [REDACTED] [REDACTED] PD ^{a,b}	2.5	5	12.5
CCI [REDACTED] PD ^{a,b}	4	5	20
Total:			243.1

Abbreviations: CCI

PD = pharmacodynamics; PK = pharmacokinetics;

TB = tuberculosis.

^a Includes 3 potential additional samples.

^b Additional assessments performed outside of full clinical laboratory evaluations.

If extra blood samples are required, the maximum blood volume to be withdrawn per subject will not exceed 550 mL.

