Appendix 6: Schedule of Assessments

Schedule of Assessments – Part A (Single Ascending Dose)

Visit Name	Screening	Check-in	Treatment period			Follow-up ^a	Early termination (if applicable)	Comment (*)
Visit No.	1		2			3		
Day No. Visit window (calendar days)	-35 to -2	-1	1	2	3	8 (±2 days)		
Trial population and eligibility								
Informed consent*	X							The ICF must be signed prior to performing any protocol-related procedures, including, but not limited to, screening evaluations.
Subject eligibility	X	X						
Demographics	X							
Medical history	X							
Height and weight	X							
Alcohol breath test	X	X						
Urine drug screen	X	X						
Serology*	X							Hep B surface antigen, hep C virus antibody, HIV antibodies.
Quantiferon™ TB Gold test	X							
Serum pregnancy test*	X							All females.
FSH*	X							All females.
Trial residency								
Check-in		X						
Check-out					X			
Nonresidential visit	X							
Treatment and randomization								
Concomitant medication and concurrent procedures	X	X	X	X	X	X		
Randomization			X					
IMP administration*			X					Subjects will be dosed in a fasted state.
Safety assessments								
Physical examination*		X			X		X	Full physical examination performed at check-in. Symptom-directed physical examination at all other times.

Visit Name	Screening	Check-in	Treatment period			Follow-up ^a	Early termination (if applicable)	Comment (*)
Visit No.	1		2			3		
Day No. Visit window (calendar days)	-35 to -2	-1	1	2	3	8 (±2 days)		
Vital signs	X	X	X*	X*	X*		X	Day 1: Predose (triplicate), 1, 2, 4, 6, 8, and 12 hours postdose. Day 2: 24 hours postdose. Day 3: 48 hours postdose. Timepoints may be adjusted based on emerging data.
Safety ECG	X	X	X*	X*	X*		X	Day 1: Predose (triplicate), 2, 4, and 8 hours postdose. Day 2: 24 hours postdose. Day 3: 48 hours postdose.
Telemetry/continuous ECG*			X*	X*				See footnote b. Day 1: 3 readings predose (-60, -45, and -30 minutes), 0.25, 0.5, 1, 1.5, 2, 3, 4, 6, 8, and 12 hours postdose. Day 2: 24 hours postdose.
All hematology, coagulation, and clinical chemistry	X	X		X*	X*		X	Day 2: 24 hours postdose. Day 3: 48 hours postdose.
Urinalysis	X	X			X*		X	Day 3: 48 hours postdose.
Urine pregnancy test*		X			X		X	Only female subjects.
Adverse events	X		X			X	X	
PK/PD assessments								
PK blood sample*			X*	X*	X*		X	See footnote c. Day 1: Predose, 0.25, 0.5, 1, 1.5, 2, 3, 4, 6, 8, and 12 hours postdose. Day 2: 24 and 36 hours postdose. Day 3: 48 hours postdose.

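### Six of the eight stopping criteria that gate the second cohort of Group A1 cannot be met by a finding in the only AQ280 sentinel, and the five laboratory ones may have no result when that cohort is dosed

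*Protocol*

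**What the plan says.** Group A1 is split into a sentinel pair, "with 1 subject receiving AQ280 and 1 subject receiving placebo", and a second cohort of six, of whom five receive AQ280 (Protocol Section 3.1.1). On timing, the same section says: "The 2 sentinel subjects (first cohort) will be dosed at least 24 hours before the second cohort of 6 subjects". The rule for proceeding is: "Dosing of subjects in the second cohort will not occur if any of the dose escalation stopping criteria" of Section 3.7 are met by the sentinels. SAP Section 3.1.1 repeats this rule.

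Two other places describe the same step in different terms. Section 3.4.1 says that the 24-hour interval "is considered sufficient, after review of available safety data". Section 5.3 says that, "providing no safety concerns arise, the remaining 6 subjects will be dosed at least 24 hours later".

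For Part A, the Appendix 6 schedule places the postdose hematology, coagulation and clinical chemistry samples at: "Day 2: 24 hours postdose. Day 3: 48 hours postdose". Section 3.7 lists eight bulleted criteria for stopping escalation. Ahead of them stand two rules that halt the study: one related SAE, or related severe AEs in two subjects of the same group.

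**The concern.** Section 3.4.1 gives the purpose of the sentinel step as limiting the consequences of unknown off-target toxicity. Its formal rule is borrowed from criteria written for a group of eight, six of them on AQ280. Two things then fail to match. Most criteria count affected subjects and need at least two, but only one sentinel receives the drug. The laboratory criteria need a result and a confirmatory repeat, but the cohort may be dosed at the time the first scheduled postdose sample is drawn.

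At stake is the first exposure of five more people to AQ280. A laboratory abnormality confined to the AQ280 sentinel would leave the five laboratory criteria formally unmet. It would count only as the first of the two cases needed, and the second could then come only from a cohort already dosed or from the placebo sentinel.

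**Working it through.** **1. Check that the laboratory schedule has been read correctly.** Appendix 6 (Part A) has full safety panels at screening, check-in, 24 h and 48 h, which is 4 draws. At 9.3 mL each, 4 × 9.3 = 37.2 mL. Protocol Appendix 3 gives 4 samples and 37.2 mL under "Full clinical laboratory evaluations". The other rows agree too: PK 14 scheduled + 3 optional = 17, and separate PD draws 5 + 3 optional = 8. So no full safety panel is scheduled between dosing and 24 h.

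**2. Classify the Section 3.7 bullets.**

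| Bullet | Data source | Subjects needed | Repeat test needed |
|---|---|---|---|
| Signs or symptoms of similar nature | Clinical observation | 2 | No |
| Liver tests | Safety laboratory | 2 | Yes |
| Creatinine | Safety laboratory | 2 | Yes |
| Hemoglobin | Safety laboratory | 2 | Yes |
| Neutrophils/platelets | Safety laboratory | 2 | Yes |
| aPTT/PT | Safety laboratory | 2 | Yes |
| Exposure limit | Predicted exposure | 1 | No |
| QTcF | ECG | 1 | Yes |

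- Laboratory bullets: 5 of 8, all needing a repeat test and two subjects.
- Bullets needing two subjects: 5 + 1 = 6 of 8.
- Bullets that one AQ280 sentinel could meet alone: 8 − 6 = 2 (exposure and QTcF).
- Adding the two halt rules gives 10 rules. Laboratory rules are then 5 of 10. Rules needing two subjects are 6 + 1 = 7 of 10, because the severe-AE halt also needs two.

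**3. Apply the two-subject requirement to the pair.** AQ280 sentinels = 1, which is fewer than 2. An abnormality in that subject alone cannot meet any of the six bullets, at 24 h, 48 h or later. Within the pair, each of the six could be met only if the placebo subject were affected as well.

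**4. Compare the timing.** The table shows scheduled postdose panels drawn before the second cohort is dosed.

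| Second cohort dosed at | Panels already drawn |
|---|---|
| 24 h (earliest permitted) | None |
| After 24 h, up to 48 h | 24 h sample |
| After 48 h | 24 h and 48 h samples |

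At the earliest permitted time, results in hand from the scheduled panel = 0 for both sentinels, and no repeat is possible. Later, the answer depends on laboratory turnaround, which the documents do not state.

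**5. Look for a rule that closes the gap.** Section 3.4.1 asks for review of whatever safety data are available. Section 5.3 asks that there be no safety concern. Section 7.3.2 permits laboratory tests to be moved or added but does not require it. None makes the 24 h result a precondition. By contrast, Section 3.6 does set a data cutoff for dose escalation: safety, tolerability and PK data up to 48 hours postdose.

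**The case against.** The strongest reply is that the formal criteria are not the only barrier, and that 24 hours is a minimum rather than a planned decision time. Both statements are true. Section 3.4.1 requires a safety review and Section 5.3 adds a test broader than any listed criterion. Under either, the investigator could wait for laboratory results or act on one abnormal value. One related SAE halts the study. By 24 hours the sentinels have had vital signs at 1, 2, 4, 6, 8 and 12 h, safety ECGs at 2, 4 and 8 h, telemetry and AE observation. The starting dose of 3 mg is also below the 10 mg predicted to be minimally active, and Section 3.4.1 argues from other JAK inhibitors that no effect is expected beyond 24 hours after a single dose.

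These facts rule out three stronger readings that a reader might infer.

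- **The gate opens by default.** It does not: the review, the no-concern condition and the halt rules all apply alongside the bullets.
- **Six of eight criteria cannot be assessed at 24 hours because PK is not yet assayed.** The exposure bullet concerns predicted exposure, and Section 3.5.1 already gives a prediction at 3 mg, so it does not depend on sentinel PK results. The six in this point are the bullets needing two subjects.
- **The laboratory criteria can never be assessed in time.** A later second cohort could use the 24 h sample. The separate PD blood samples at 1, 4, 8 and 12 h have redacted analytes and might include some that the criteria use, although nothing links them to the gate.

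The mismatch itself survives. Discretion to wait is not a requirement to wait, and a low starting dose does not make a two-subject criterion applicable to one AQ280 subject. The class argument in Section 3.4.1 rests on pharmacodynamic effects, whereas the sentinel step is there for off-target toxicity.

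**Conclusion.** The concern holds as a mismatch between the rule cited for the sentinel step and the pair to which it is applied. The two-subject requirement disables six of eight bullets for a finding confined to the AQ280 sentinel. This does not depend on timing or on any redacted content. The timing gap affects the five laboratory bullets and is certain only at the earliest permitted moment; how long it lasts depends on an unstated turnaround. It assumes that the redacted PD samples do not supply confirmed values of the same analytes.

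The documents do not show that the second cohort would be dosed without safety review. They do show that the written criterion for a first-in-human safety step is largely one the AQ280 sentinel alone could not trigger. That is a fault in the rule and not merely a missing detail, and it should be corrected.

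**What to change.** Reconcile Protocol Sections 3.1.1, 3.4.1, 3.7 and 5.3 with one another and with the Appendix 6 laboratory times, so that:

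- the criteria cited for the sentinel gate can be applied to a pair with one AQ280 subject;
- they rest on data that exist when the gate opens;
- the three descriptions of the gate state the same condition and name the results that the review covers.

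The design summary in SAP Section 3.1.1 should follow. How to achieve this is for the sponsor and investigator to decide; no interval, threshold or clinical rule is proposed here.

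The cost is protocol wording and possibly some delay to one cohort of one group. The length of any delay cannot be estimated because laboratory turnaround is not given. Reconciling the text does not in itself call for more subjects.

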3.1.1.1. Food Effect Evaluation

Subjects in the food effect evaluation group will participate in 2 treatment periods, with the same treatment (AQ280 or placebo) administered in both periods. Period 1, Day 1 dose will be administered in the fasted state in accordance with a randomization schedule and Period 2, Day 1 dose will be given 30 minutes after starting a standard high-fat breakfast (see [Section 6.2](#)). The dose administrations in the 2 treatment periods will be separated by a washout of ≥ 7 days.

An overview of the study design for Part A, food effect evaluation, is shown in [Figure 3](#).

Figure 3: Study Schematic (Part A, Food Effect Evaluation)

Abbreviation: PK = pharmacokinetics.

Note: If conduct of Period 2 is delayed, a safety follow-up phone call may be done 1 week (± 2 days) after dosing in Period 1.

The total duration of study participation for each subject (from screening through safety follow-up visit) is anticipated to be approximately 6 weeks. For the food effect evaluation group, up to approximately 8 weeks, including screening and safety follow-up, is anticipated for each subject.

Schedules of Assessments for Part A and for Part A food effect evaluation are presented in [Appendix 6](#).

3.1.2. Part B (Multiple Ascending Dose)

Part B will comprise a multiple-dose, sequential group, escalating-dose design conducted in healthy adult male and female subjects. Part B may start prior to completion of all planned dose groups in Part A, at a dose equal to or less than that evaluated as safe and well tolerated in Part A.

A total of approximately 24 subjects are planned to be studied in 3 groups (Groups B1 to B3). In each group, 6 subjects will receive AQ280 and 2 subjects will receive placebo. Each group should contain both male and female subjects, preferably at least 2 subjects of each gender. Additional groups may be added based on the need for more evaluations or groups removed based on data obtained.

There will be a minimum of 9 days between dose escalations for each group.

Potential subjects will be screened to assess their eligibility to enter the study from 2 days up to 5 weeks before the first dose of AQ280 or placebo. Each subject will participate in 1 group only and reside at the study site from Days -1 to 9.

For all subjects, dosing is planned to be QD on Days 1 to 7, inclusive, at approximately the same time each morning. The dosing regimen in Part B may be changed following review of preliminary data from groups in Part A or previous groups in Part B. The daily dose administered, when given repeatedly, will be predicted to not exceed an exposure shown to be safe and well tolerated in Part A. Dietary state will be determined based on data obtained in Part A.

A safety follow-up visit will be conducted 1 week (± 3 days) after the final dose.

Based on the ongoing review of the safety, tolerability, and PK results, additional outpatient visits may be required.

[figure not shown]
Safety assessments will include AE reporting, vital signs, ECGs, clinical laboratory tests, and physical examination.

Blood samples to determine the PK of AQ280 and its main metabolite, AQ282, will be collected from predose up to 24 hours postdose on Day 1; predose on Days 3 through 6; and from predose up to 48 hours postdose on Day 7.

Urine samples will be collected at intervals for the purpose of metabolite profiling.

An overview of the study design for Part B is shown in [Figure 4](#).

Figure 4: Study Schematic (Part B)

Abbreviations: PK = pharmacokinetics; QD = once daily.

The total duration of study participation for each subject (from screening through follow-up visit) is anticipated to be approximately 7 weeks.

A Schedule of Assessments is presented in [Appendix 6](#).

3.2. Study Start and End of Study Definitions

The start of the study is defined as the date the first subject signs an informed consent form (ICF). The point of enrollment occurs at the time of subject number allocation. The end of the study is defined as the date of the last subject's last assessment (scheduled or unscheduled).

3.3. Additional Groups

Following review of the safety, tolerability, and PK data, additional dose groups (where systemic exposure is not expected to exceed that stated in the dose escalation stopping criteria [[Section 3.7](#)]) may be added to the study. Up to 3 further groups of 8 subjects (6 active:2 placebo) may be included in each of Parts A and B. There will be no further dose escalation in these additional groups if dose escalation stopping criteria have been met, and a dose level cannot be repeated if it previously met a stopping criterion. The requirement for additional groups will be agreed with the sponsor and dose escalation committee (DEC) and documented in the trial master file (TMF).

3.4. Discussion of Study Design, Including the Choice of Control Groups

For both parts of the study, a sequential group, ascending dose design has been chosen for safety reasons as AQ280 is in the early stages of clinical development, with Part A of the study being the first time it will be administered to humans. Oral doses have been chosen for both parts of the study, as this is the intended clinical route of administration. A 2-period crossover design has been chosen for the food effect evaluation, as this gives a within-subject assessment of the influence of food on the PK of AQ280 and so increases the power of the study for the given number of subjects.

It is the intent of Part B to dose subjects such that steady state plasma levels of AQ280 are achieved and maintained for several days. Based on the available nonclinical data, it is expected that this will be achieved within 7 days of QD dosing; however, a full review of all available safety, tolerability, and PK data from Part A will be performed to confirm the dose

regimen for Part B. If the apparent terminal elimination half-life ($t_{1/2}$) of AQ280 is shorter or longer than predicted by the nonclinical data, further dose escalation may be required to include a revised dose regimen. This revised dose regimen will be agreed upon by the sponsor and DEC.

Details of the dosing regimen and duration used for Part B of the study will be documented in the TMF.

A 48-hour period of residency after single dose in Part A and final dose in Part B is expected to correspond to $\frac{C}{Cl}$ half-lives of AQ280.

Based upon the nonclinical data, the duration of each treatment period is considered adequate to achieve the study objectives. An interval of at least 7 days between dose administrations in the 2 treatment periods in the food effect evaluation is considered adequate to prevent carryover of AQ280.

This study will be double blind and placebo controlled in order to avoid bias in the collection and evaluation of data during its conduct. Placebo has been chosen as the control treatment to assess whether any observed effects are treatment related or simply reflect the study conditions.

Conducting the study in healthy subjects mitigates the potential confounding effects of the disease state and concomitant medications. Subjects with history of any significant infectious disease are excluded to mitigate the potential risk of infection. Light smoking during the trial is permitted, as this is not expected to interfere with AQ280.

